5.1.3.1 End of Study (or Early Termination)

Upon completion of the ad libitum product use session on Day 4, subjects will undergo end of study assessments and be released from the site. The following end-of-study procedures will be completed:

- Conduct brief physical examination (symptom driven)
- Review concomitant medications and AEs
- Provide tobacco-cessation information (Quit Assist™ website referral)

5.2 Study Procedures

5.2.1 Informed Consent

All prospective subjects will have the study explained by the investigator or their designee.

All prospective subjects will be required to read, sign, and date the ICF before any screening or study procedures are performed. Written acknowledgment of the receipt of full informed consent and the subject's freely tendered offer to participate will be obtained from each subject in the study and documented in the source documents. Each subject will receive a signed and dated copy of the ICF.

5.2.2 Tobacco/Nicotine Product-Use History

Subjects will be required to report tobacco product and nicotine product-use histories to satisfy study inclusion and exclusion criteria.

Characteristics of the subject's usual e-vapor products will be documented in the Tobacco and Nicotine Use History Questionnaire.

5.2.3 Medical History and Demographics

Medical history and demographic data, including sex, age (each subject must show proof of age with government-issued identification [e.g., driver's license], which will

be photocopied as source documentation), race, and ethnicity, for each subject will be recorded.

5.2.4 Questionnaires

Self-administered questionnaires will be completed at various times throughout the study (see [Table 1](#)) with trained site staff present for assistance. The questionnaires to be used in this study are as follows:

- Demographics Questionnaire, Visit 1 (screening)
- Tobacco and Nicotine Product-Use History Questionnaire, Visit 1 (screening)
- Use the Product Again Questionnaire, Visit 2: Day 1 through Day 4

5.2.5 Physical Examination

All physical examinations will be conducted by the investigator or their designee (licensed physician). A general physical examination including observations and questioning by the investigator/ or the investigator's designee (licensed physician), will be completed at Visit 1 (screening). A symptom-driven physical examination will be performed at End-of-Study or Early Termination and at other times as necessary to evaluate AEs or other subject complaints. All findings will be documented.

5.2.6 Height, Weight, and Body Mass Index

Height (cm) and weight (kg) will be measured with subjects wearing indoor clothing with shoes off. BMI will be calculated as weight (kg)/height (m^2).

5.2.7 Electrocardiogram

A 12-lead ECG will be performed after subjects have rested in a supine position for at least 5 minutes and at least 15 minutes after last tobacco or nicotine product use. The ECG will be documented as normal, having a not clinically significant abnormality, or having a clinically significant abnormality. In addition, ventricular rate, PR interval, QRS duration, and QT interval (corrected using Fridericia's formula and uncorrected) will be noted on the CRF.

5.2.8 Clinical Laboratory Tests

The clinical laboratory tests listed below and performed at screening and other time points as applicable (see [Table 1](#)) will be conducted by a local laboratory accredited by the Centers for Medicare and Medicaid Services (Clinical Laboratory Improvement Amendments of 1988 [CLIA-88]). Analyte values must fall within laboratory normal ranges or be deemed “not clinically significant” in the opinion of the investigator or the investigator’s designee (licensed physician). Parameters to be evaluated are as follows:

- Clinical chemistry (at least 8 hours fasting): albumin, alkaline phosphatase, alanine aminotransferase, aspartate aminotransferase, bicarbonate or total carbon dioxide, blood urea nitrogen, chloride, creatinine (creatinine clearance will be calculated using Cockcroft-Gault formula at screening only), glucose, potassium, sodium, total bilirubin, total protein, and uric acid.
- Hematology: hematocrit, hemoglobin, platelet count, red blood cell count, and white blood cell count with differential.
- Urinalysis: bilirubin, blood, glucose, ketones, leukocyte esterase, nitrite, pH, protein, specific gravity, and urobilinogen. (A microscopic examination will be conducted if protein, leukocyte esterase, nitrite, or blood are detected. Microscopic analysis will include red blood cells, white blood cells, casts, and bacteria.)
- Serology: HIV, HBsAg, and HCV antibody screenings.
- Urine cotinine: a positive test will be required (≥ 500 ng/mL) for participation in the study.
- Pregnancy: serum or urine human chorionic gonadotropin (all females only) as appropriate (Section [5.2.9](#)).
- Follicle-stimulating hormone: postmenopausal females only.
- Urine drug screening: amphetamines, phencyclidine, opiates, cannabinoids, and cocaine (Section [5.2.10](#)).
- Alcohol screening: ethanol breath test or urine screening (Section [5.2.11](#)).

5.2.9 Pregnancy Test

Urine or serum pregnancy tests will be completed by the clinical site staff at Visit 1 (serum) and check-in Visit 2 (urine). A positive test result will eliminate subjects from further participation in the study.

5.2.10 Urine Drug Screen

Urine drug screens will be completed by the clinical site staff for drugs of abuse (amphetamines, phencyclidine, opiates, cannabinoids, and cocaine) at Screening and Check-in for each visit. Positive test results (for any reason) will eliminate subjects from further participation in the study.

5.2.11 Alcohol Urine or Breath Test

A urine or breath alcohol test will be performed at Screening and Check-in for each visit. A positive test result will eliminate subjects from further participation in the study.

5.2.12 Vital Signs

Vital signs (respiratory rate, pulse rate, blood pressure, and oral temperature) will be assessed with subjects in the sitting position after at least 5 minutes of rest and at least 15 minutes after last tobacco use.

5.2.13 Analytical Methodology

5.2.13.1 Clinical Laboratory

Values for clinical laboratory parameters will be determined by clinical laboratory facilities accredited by the Centers for Medicare and Medicaid Services (CLIA-88). Hematology, clinical chemistry, and urinalysis will employ standard clinical laboratory procedures.

5.2.13.2 Exhaled Breath Collection

Exhaled breath condensate samples will be collected using the special exhaled breath sample-collection system provided by Enthalpy Analytical. A fresh Single-Subject Longitudinal Sampling Kit will be used for each sample.

The mouth piece on the collection tubes will be replaced between replicated measurements. The hand-held collection portion of the device may be reused between subjects, as long as the mouth piece has been replaced.

Exhaled breath condensate samples will be collected on a particulate filter located immediately beyond the mouth piece and followed by a cryogenically cooled trap. After sample collection is completed, the special exhaled breath sample-collection system will be transported to the on-site laboratory for processing.

The particulate filter will consist of a 44-mm glass fiber pad housed in a plastic filter holder. The filter will be removed from the holder and used for measurement of propylene glycol, glycerin, menthol and nicotine. The liquid in the cryogenically cooled trap will be removed from the special exhaled breath sample-collection system and analyzed for propylene glycol, glycerin, and nicotine. A separate sample will be collected for measurement of aldehydes in exhaled breath samples. The particulate filter will consist of a 44-mm glass fiber pad housed in a plastic filter holder treated with 2,4-dinitrophenylhydrazine and analyzed for aldehydes. The liquid in the cryogenically cooled trap will be removed from the special exhaled-breath sample-collection system, treated on-site with 2,4-dinitrophenylhydrazine, and analyzed for aldehydes.

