3.2 Endpoints

The following study endpoints will be assessed:

- Primary endpoint: total amount of nicotine, glycerin, propylene glycol, menthol, formaldehyde, acetaldehyde and acrolein in exhaled breath for four e-vapor products (sham value corrected).
- Secondary endpoints: cartridge weight changes (before and after exhaled breath sessions), cartridge weight changes per cartridge and in total during 12 hours of ad libitum use, puff count, average puff flow rate, average puff volume and average puff duration per cartridge and in total by subject during 12 hours of ad libitum use, responses to Use Product Again Questionnaire.

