7.0 EVALUATION OF RESPONSE PARAMETERS**7.1 ANALYSIS OF PRIMARY RESPONSE ENDPOINTS**

Sham and test product-derived sample amount of each analyte as well as sham-corrected amount (SCA) of each analyte will be summarized, by test product, per Section 4.1. Sham-corrected analyte amounts will be computed by subtracting corresponding sham response values from test product response values.

Mixed effects ANCOVA models will be fit to separately to the following sham-corrected amount of 7 analytes that will be measured in exhaled breath repeatedly in each subject over the 4 days of Visit 2:

1. Nicotine
2. Glycerin
3. Propylene glycol
4. Menthol
5. Formaldehyde
6. Acetaldehyde
7. Acrolein

The Minimum Detection Limit (MDL) of each analyte is provided in Table 4.

Table 4. Limits of Detection for Exhaled Breath Analytes

Analyte	Nominal MDL (μg)
Propylene glycol	5
Vegetable glycerin	5
Nicotine	0.5
Menthol	0.5
Formaldehyde	0.2
Acetaldehyde	0.2
Acrolein	0.2

Statistical Analysis Plan

Analyte concentrations that are below the Minimum Detection Limit (MDL) will be set to the MDL value for analyses.

Two types of sampling containers were used for collection of the analytes from each subject's exhaled breath (Table 5). Sampling container 1 with one tube and one pad was used for capturing nicotine, glycerin, propylene glycol, and menthol while Sampling container 2 with one tube and 2 pads was used for capturing formaldehyde, acetaldehyde, and acrolein. Exhaled breath samples were collected in 2 independent sampling sessions, separated by 45 minutes, within each period (Figure 1B). Sampling container 1 was used to trap exhaled breath in the first sampling session, while sampling container 2 was used in the second sampling session.

There are two subsamples (1 tube + 1 pad) of each analyte, in each sampling container 1 and three subsamples (1 tube + 2 pads) of each analyte in sampling container 2. Enthalpy Analytical Company will provide data sets with the tube and pad analyte amount from each of the two types of Sample container, for each subject. Pad and tube MDL values of the same analyte will be different from one another. For each sampler, the final amounts for a given analyte will be computed in one of three ways:

1. When both the amounts of analyte in pad(s) and tube are above MDL, the exhaled breath sample (EBS) value will be the sum of the pad and tube values

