2. When the amounts of analyte in pad(s) and tube are both below MDL; EBS value will be the sum of the two MDL values. However, since the MDL is volume dependent, the sum will be considered as below MDL (i.e. <0.5).
3. When the amount of one analyte is MDL, but the other is above MDL. EBS will be the sum of the MDL value and the above BLLOQ value.

Descriptive statistics (number of observations, number of missing, mean, SD, median, minimum, maximum, the first quartile, the third quartile, 95% confidence interval, and coefficient of variation) will be tabulated for each of these analytes by test product. Frequency (n and %) of MDL values will be summarized for each product. If the percentage of MDL values for an analyte is more than 50% in any product group, the analyte will not be analyzed with a mixed model.

Statistical Analysis Plan

Each mixed model will be fit to the data by restricted maximum likelihoods. Covariance structures to account for dependencies among repeated measures, within subjects, will be selected for each model using AIC criteria.^[11] Four candidate covariance structures will be considered: compound symmetry, 1st order autoregressive, 1st order autoregressive with a random subject effect, and unstructured. Each model will include period-specific sham values (as a covariate), sequence, study product, and period as fixed effects; subjects nested within-sequence will be modeled as random effects. Standard residual analyses will be used to examine validity of assumptions for the fixed effect distributions. Response variables will be appropriately transformed (e.g., log, reciprocal, or square root) if the residuals indicate distributional assumptions don't hold. The models will be refit to the transformed data and residual analyses again be performed verify that the transformations corrected the problems.

Mean SCA response with (95% confidence limits), for each test product, will be estimated using SAS Least square means methods in each model. Estimates will be back-transformed to the original scale as necessary. Analyte LSmean estimates (with 95% CIs) for each test product will be tabulated for each model. As an example, the SAS Proc Mixed code to fit the Mixed effects ANCOVA model [with an AR(1) covariance structure] is provided below:

```
ods graphics on;
proc mixed data=evap_data method=REML;
  class seq test_product period subject;
  model Analyte = sham § seq period test_product/residual DDFM=KR;
  Random subject (seq); †

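### The protocol omits menthol from the cold-trap assay while the SAP adds a tube value for it, so the content of the menthol total is unsettled

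*Protocol*

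**What the plan says.** Protocol 3.2 defines the endpoint as a sham-corrected total: "Primary endpoint: total amount of nicotine, glycerin, propylene glycol, menthol", followed by the three aldehydes. Protocol 5.2.13.2 describes two fractions for container 1. The glass-fibre filter is "used for measurement of propylene glycol, glycerin, menthol and nicotine". The liquid from the cooled trap behind it is "analyzed for propylene glycol, glycerin, and nicotine". For container 2, the same section has both filter and trap liquid analysed for aldehydes.

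SAP 7.1 states the sample structure without exception: "There are two subsamples (1 tube + 1 pad) of each analyte, in each sampling container 1". It expects both amounts from the laboratory: "Enthalpy Analytical Company will provide data sets with the tube and pad analyte amount". It then gives three rules for combining them. When both are above the minimum detection limit (MDL), "the exhaled breath sample (EBS) value will be the sum of the pad and tube values". When both are below, the two MDLs are summed and the result counts as below MDL. When only one is below, "EBS will be the sum of the MDL value and the above BLLOQ value". It adds: "Pad and tube MDL values of the same analyte will be different from one another". The separate pad and tube MDLs are not given; Table 4 of the SAP gives one nominal value for menthol, 0.5 µg.

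**The concern.** Six of the seven primary analytes are assayed in both fractions under the protocol. Menthol alone is assayed in one. Yet the SAP builds its final amount from two fractions and assumes a tube result, above or below MDL, in every rule.

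If the protocol list is what the laboratory does, two things follow. Any menthol that reaches the trap is left out of a result labelled as a total, and that error can only run downward. The data are meant for a model of exposure to non-users, where an understated amount is the less cautious error. Second, the SAP cannot be carried out for menthol as written. The programmer would have to choose between a missing sum, an MDL put in place of an unmeasured fraction, and the pad value alone. These give different tables, and the SAP does not say which applies.

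**Working it through.** Neither document states a figure on this point, so there is none to reproduce. I take the SAP's tube to be the protocol's cold trap; neither document says so outright, but no other second fraction is described.

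**Step 1: set the lists side by side.**

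| Analyte | Filter/pad, Protocol 5.2.13.2 | Trap liquid, Protocol 5.2.13.2 | SAP 7.1 |
|---|---|---|---|
| Propylene glycol | yes | yes | pad + tube |
| Glycerin | yes | yes | pad + tube |
| Nicotine | yes | yes | pad + tube |
| Menthol | yes | not listed | pad + tube |
| Three aldehydes | yes | yes | pads + tube |

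Protocol 5.2.14 lists menthol under Trapping Container 1 but does not name the fraction, so it does not settle the matter.

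**Step 2: trap not assayed, pad value used alone.** Let f be the share of exhaled menthol that passes the filter, taken as equal in product and sham samples. The sham-corrected amount (SCA) is product minus sham, so

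pad-only SCA = (1 − f) × true SCA.

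The documents do not give f. Over an assumed range:

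| f | pad-only SCA / true SCA | understatement |
|---|---|---|
| 0 | 1.00 | 0% |
| 0.05 | 0.95 | 5% |
| 0.10 | 0.90 | 10% |
| 0.25 | 0.75 | 25% |
| 0.50 | 0.50 | 50% |

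**Step 3: trap not assayed, an MDL m entered as the tube value.** With pad values P (product) and S (sham),

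SCA = (P + m) − (S + m) = P − S.

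Take m = 0.5 µg (the nominal MDL, used as a stand-in for the unstated tube value), S = 0.5 µg and illustrative values of P:

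| P (µg) | product amount with m | inflation of product amount, m/P | SCA without m | SCA with m |
|---|---|---|---|---|
| 2 | 2.5 | 25% | 1.5 | 1.5 |
| 10 | 10.5 | 5% | 9.5 | 9.5 |
| 50 | 50.5 | 1% | 49.5 | 49.5 |

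The sham amount goes from 0.5 to 1.0 µg. So the sham and product amounts, which SAP 7.1 summarises separately, are inflated, while the SCA is not. Nor does this substitution recover any menthol lost to the trap: the SCA is still the pad-only value of Step 2.

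Cancellation needs the same m in both samples. The SAP calls the MDL volume dependent, so it may be only approximate. The extreme case, m added to the product sample only, shifts the SCA by 0.5 µg: 0.5/1.5 = 33.3%, 0.5/9.5 = 5.3% and 0.5/49.5 = 1.0%.

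**Step 4: trap assayed for menthol.** Pad plus tube is then the total, the SAP rules work as written, and the only error is the short list in the protocol.

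**Step 5: where the result appears.** Protocol Table 2 lists Products A and B as non-menthol. SAP 7.1 drops an analyte from the mixed model if more than 50% of its values are at the MDL in any product. Menthol may therefore reach the report only through descriptive summaries. The definition of the menthol amount would then carry the whole result for Products C and D.

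**The case against.** The best case on the other side is that the protocol sentence is simply incomplete. The SAP is dated 05 JUN 2017, after the protocol's 02 MAR 2017. It is more specific about the sampler: it gives container 2 two pads where the protocol describes one filter, and it speaks of the containers in the past tense. It says the laboratory will supply tube and pad amounts for both container types and that their MDLs differ, and it does not single menthol out. On that account the laboratory measures menthol in the tube and the SAP total is correct.

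This is plausible and cannot be ruled out. It is not shown either: the SAP does not say that the assay was changed or extended. The objection therefore removes any claim that bias is established, but leaves the contradiction.

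A reader might infer that the menthol endpoint must be either understated or padded. The documents do not support that, for three reasons. The case in Step 4 gives a correct total. Understatement also needs menthol to pass the filter, on which the documents are silent. And the MDL rules cover measured fractions below the limit, so entering an MDL for an unassayed tube would misapply them; done equally in sham and product, it would not pad the sham-corrected endpoint. Nor do the documents support a range that starts at 10%, since f could be 0.

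**Conclusion.** The concern holds as an unresolved contradiction about a primary endpoint, with a possible but unquantified downward bias. Protocol 5.2.13.2 and SAP 7.1 describe different menthol measurements, and the SAP has no valid tube term if the protocol list is followed. In that event sham-corrected menthol is low by f, mainly for Products C and D. The values of 0 to 50% above are an assumed range, not an estimate. If the laboratory assays menthol in the tube, there is no bias and the protocol text alone needs correcting. The other six analytes are not affected. The point should be settled before the menthol results are computed, because the choice changes both the number and what it may be called.

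**What to change.** Ask the laboratory whether menthol is assayed in the container 1 trap liquid, and make the two documents agree.

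- **Preferred:** add menthol to the analytes listed for the container 1 trap liquid in Protocol 5.2.13.2, using liquid that is already collected. The SAP sum is then valid as it stands. If the assay is already done, this is only a text correction; otherwise it costs one more analyte on an existing sample. Whether that liquid suits a menthol assay is for the laboratory to confirm, as the documents do not say.
- **If the liquid cannot be assayed for menthol:** state in SAP 7.1 that menthol is pad only, apply no tube MDL, and label it in tables, and in the input to the exposure model, as filter-captured menthol rather than total. The cost is a few lines of SAP text and a narrower claim for the menthol result.

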5.2.14 Analysis of Exhaled Breath Samples

The following constituents will be measured in the exhaled breath samples:

- Trapping Container 1: propylene glycol, glycerin, nicotine, menthol
- Trapping Container 2: formaldehyde, acetaldehyde, acrolein

The actual time and type of sample collection will be documented.

Samples will be shipped to the following:

Enthalpy Analytical, Inc.
[name]
[name]
[contact]
[contact]
www.enthalpy.com

5.2.15 12 hour ad libitum Product Use Session

The “BVR2.3 REV05 w/ topography v2 battery” will be used during the 12-hour ad libitum topography session. All devices will be fully charged, cleared, and time reset prior to dispensing (within 24hrs, specific USB adaptor and connection to a computer is required). The subjects will use a “BVR2.3 REV05 w/ topography v2 battery” for all EVP use during the 12 hours. The use of the “BVR2.3 REV05 w/ topography v2 battery” is transparent to the user and collects the date, time, duration of each puff, puff flow rate, as well as the battery voltage during each puff. All “BVR2.3 REV05 w/ topography v2 batteries” data will be downloaded via the topography battery specific USB connector by the site staff and transferred to Cato Research for analysis.

- The subjects will be instructed, according to product insert, that “when the battery needs to be recharged, the LED tip will blink rapidly and repeatedly” and “when the cartridge is almost empty, you will notice a reduction in flavor and vapor.” The subjects will be instructed to inform the site staff when either event occurs.
- When the battery needs to be recharged, the site staff will replace the depleted “BVR2.3 REV05 w/ topography v2 battery” with a freshly charged (within 24hrs) “BVR2.3 REV05 w/ topography v2 battery” using the same cartridge.
- When the cartridge is almost empty the site staff will replace with a freshly charged (within 24hrs) “BVR2.3 REV05 w/ topography v2 battery” and new cartridge.
- The site staff will document each “BVR2.3 REV05 w/ topography v2 battery” used with each cartridge and time of changing the “BVR2.3 REV05 w/ topography v2 battery” or “BVR2.3 REV05 w/ topography v2 battery” and cartridge.

5.2.16 Tobacco-Cessation Information

The investigator or designee at Screening and at the End-of-Study or upon Early Termination will advise all adult tobacco users that to reduce the health effects of using tobacco products, the best thing to do is to quit. The investigator or their designee will also refer all adult tobacco users to the Quit Assist™ website, which contains citations to a number of third-party information sources, including websites, telephone resources, and other organizations with additional information.

